3.6. Randomisation

Patients will be randomised once baseline data collection is complete. The randomisation sequence will use blocks of random sizes (from 2 to 8 which will be unknown to the research team members involved in recruitment) to prevent the research team from predicting the randomisation sequence. The allocations will be concealed using sequentially numbered, opaque, sealed envelopes. These envelopes will be opened sequentially after obtaining all patients' consent and, their names and other details have been written on the appropriate envelope. The use of envelopes and participant allocation will be monitored to ensure that the envelopes are used in the correct sequence.

3.7. Intervention

This will take place in an outpatient context after the patient has been recruited and randomised:

1. Participants will be offered the opportunity to complete an ACP by a nurse trained as an ACP facilitator, who will discuss the process with them using the booklet, "Your life and your

choices: plan ahead,” produced by the Northern Ireland Public Health Agency and Macmillan Cancer Support³³. At this stage, the ACP nurse will ask the participant to complete the ‘Record of my wishes’ form found in the booklet.

2. One-to-two weeks later, they will complete an ACP document ([Advance Care Planning Summary](#)) with the help of the ACP facilitator, working together with trained expert patients who (if the patient wishes) will provide peer support at the time of ACP completion and subsequently by telephone ^{10,24,34,35}, assisted where necessary by the ACP facilitator.
3. The patient’s nominated relative/friend will also be invited to take part in the discussion if the patient wishes and the relative/friend agrees.
4. The ACP document will be based on that used within the BHSCT (“A record of my wishes”, recently developed by the Northern Ireland Palliative and End of Life Care Implementation Group and based on the booklet, “Your life and your choices: plan ahead”), resulting in the completion of the [Advance Care Planning Summary, alongside](#) the identification of a nominated person to help in decision-making as well as the following:
 - a) What the patient would like to happen in the future
 - b) What the patient would not want to happen
 - c) Recording the presence and broad content of an ADRT if it already exists
 - d) Preferred place of care at the end-of-life
 - e) Special requests

The patient will be encouraged to keep the ACP with them and to make it available to anyone caring for them. A summary of the patient’s wishes in the ACP will be kept with their medical notes and copied to their GP, relevant social and community services, and to out-of-hours and ambulance services. The ACP will be reviewed if circumstances change or the patient changes their mind, and in any case after twelve weeks. Participants in the deferred entry group will be offered the intervention twelve weeks after the immediate entry group. ACP implementation will be informed by a realist review of the literature³⁶ and draw on the Consolidated Framework For Implementation Research,³⁷ which focuses on intervention characteristics, organisational setting, and the characteristics of the individuals involved.

NB: Patient’s normal hospital care is not affected during the trial and they have the right to withdraw at any time.

3.8. Outcome Data collection

RCT outcome measures

1. Quality of life as measured by the Kidney Disease Quality of Life instrument – Short Form (KDQOL-36TM)⁴⁰
2. Degree of cognitive impairment as measured by the Isaacs Set Test (IST 15)⁴¹
3. Degree of anxiety, depression, well-being, functioning and risk as measured by the Clinical Outcomes in Routine Evaluation measure (CORE 34)⁴²
4. The degree to which the patient felt that they had shared in decision-making about their care as measured by the Patient Experience of Shared Decision Making (SHARED) instrument⁴³
5. Agreement between the patient and their nominated relative/friend in terms of the patient's preferences. We will measure this by asking the carer to make an independent assessment of the patient's preferences in relation to the key information covered by the ACP intervention (a-e above), before taking part in the ACP.
6. An economic evaluation of costs and benefits of the ACP intervention will be conducted utilising data collected from the following sources:
 - a. Electronic hospital admissions and outpatient data for each patient
 - b. Patient completed cost diaries documenting health and social care resource use
 - c. Patient quality of life data using the SF-12 (contained within the (KDQOL-36TM)⁴⁰)

Resource use will be valued according to appropriate tariffs, allowing comparison of mean costs per patient by group allocation for the 12 week period of the trial.

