1.6 Table 3: World Health Organisation Trial Registration Data Set

Data Category	Information
Primary registry and trial identifying number	ClinicalTrials.gov: NCT02631200
Date of registration in primary registry	October 28, 2015
Source(s) of monetary or material support	Dunhill Medical Trust
Primary sponsor	Queen's University Belfast
Contact for public and scientific queries	[name] [name]; [contact]
Public title	Advance Care Planning With Older Patients Who Have End-stage Kidney Disease
Scientific title	Advance Care Planning With Older Patients Who Have End-stage Kidney Disease: Feasibility of a Deferred Entry Randomised Controlled Trial Incorporating a Mixed Methods Process Evaluation
Countries of recruitment	Northern Ireland, United Kingdom
Health condition(s) or problem(s) studied	Advance care planning, kidney failure, chronic
Intervention(s)	Behavioural: Advance care plan
Key inclusion criteria	
 Attending the renal units taking part in the study Receiving renal replacement therapy (RRT) Capacity to understand, retain, and weigh the necessary information and communicate their decisions Identified by their consultant as having worsening symptoms, functional decline, and two or more co-morbidities
Key exclusion criteria	
 Expected to die in the next three months
Study type	Interventional
Date of first enrolment	December 2016
Target sample size	80 (patients and relative/friends)
Recruitment status	Not yet recruiting
Primary outcome(s)	Quality of life: measured by the Kidney Disease Quality of Life instrument - Short Form (KDQOL-36™)
Key secondary outcomes	
 Agreement between the patient and their nominated relative/friend in terms of the patient's preferences: measured by asking the relative/friend to make an independent assessment of the patient's preferences in relation to the key information covered by the ACP intervention, before taking part in the ACP Depression: measured by the Clinical Outcomes in Routine Evaluation measure (CORE 34) The degree to which the patient felt that they had shared in decision-making: measured by the Patient Experience of Shared Decision Making (SHARED) instrument

2. Introduction

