3.9. Timeline of Trial Outcome Measures

3.9.a. Immediate Entry Group

Baseline/Time 1: Following enrolment and prior to receiving the intervention, patients randomised to the immediate intervention group will complete the IST 15, CORE 34, and KDQOL-36TM, and SHARED. Their nominated relative/friend will make an independent assessment of the patient's ACP preferences before the patient receives the information booklet. Subsequently, the patient and (if the patient wishes) the relative/friend will participate in the ACP intervention.

Time 2: At two weeks following the intervention, the patient will complete the CORE 34 and SHARED, and review their ACP. The nominated relative/friend will make a second independent assessment of the patient's preferences.

Time 3: At 12 weeks the patient will again complete CORE 34, KDQOL-36™, and SHARED and both patient and relative/friend will review the ACP and make any desired changes.

3.9.b. Deferred Entry Group

Patients (and their nominated relative/friends) randomised to the deferred entry group will have outcomes measured contemporaneously with the immediate entry group but receive the intervention only after they have completed three sets of data i.e. at 12 weeks following entry to the trial. At 24 weeks the deferred entry group patients will again complete CORE 34, KDQOL-36™, and SHARED and both patient and relative/friend will review the ACP and make any desired changes. The deferred entry group may have more than one ACP review with the ACPN, however data will only be collected from this group at the final review.

Table 5: Schedule of Trial Interventions and Assessments

Time points	Immediate entry		Deferred entry	
	Patient *	Relative	Patient*	Relative/friend
t₁ baseline	IST 15 CORE 34 KDQOL-36™ SHARED	ACP agreement questionnaire	IST 15 CORE 34 KDQOL-36™ SHARED	
	ACP intervention	ACP intervention		
2/52	ACP 1 st review CORE 34 SHARED	ACP agreement questionnaire (before review) ACP review**	CORE 34 SHARED	
	CORE 34 KDQOL-36™ SHARED ACP 2 nd review	ACP agreement questionnaire (before review) ACP review**	CORE 34 KDQOL-36™ SHARED	ACP agreement questionnaire
24/52			ACP intervention	ACP intervention
			ACP review**	ACP agreement questionnaire (before

		CORE 34 KDQOL-36™ SHARED	review) ACP review**

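### Section 3.8 and Table 3 define the agreement outcome as a pre-ACP assessment, which conflicts with the post-ACP questionnaires scheduled in section 3.9.a and Table 5

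*Combined protocol and SAP*

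**What the plan says.** Section 3.8 item 5 gives agreement as a trial outcome. The relative/friend judges the patient's preferences "in relation to the key information covered by the ACP intervention (a-e above), before taking part in the ACP". Table 3 lists the same measure among the key secondary outcomes with the same timing: "in relation to the key information covered by the ACP intervention, before taking part in the ACP". Neither place names a time point after the intervention.

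Section 3.9 sets out when outcomes are collected. In the immediate group the first assessment is of the patient's "ACP preferences before the patient receives the information booklet". Time 2 then follows ACP: "At two weeks following the intervention, the patient will complete the CORE 34 and SHARED, and review their ACP". At that visit, "The nominated relative/friend will make a second independent assessment of the patient"'s preferences. Table 5 shows "ACP agreement questionnaire (before review) ACP review" for this group at 2 weeks and again in the next row. That row also holds the KDQOL-36 and the second ACP review, so it corresponds to Time 3 at 12 weeks. In the deferred group, Table 5 shows one agreement questionnaire at 12 weeks, ahead of that group's ACP, and another after ACP, before the later review.

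Section 4.1.b plans a 12-week analysis of covariance for CORE 34, KDQOL-36 and SHARED and does not list agreement. Section 4.2.b offers agreement as an example of a primary endpoint for cost-effectiveness. The list of benefits in section 4.2 includes the proportion of patients with a unit increase in SHARED or agreement, with the choice left open.

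**The concern.** An outcome definition should identify the observation that is to be analysed. Here it identifies one made before the relative/friend has been exposed to ACP, so it points away from the forms that could register a change. Items 1 to 4 of section 3.8 carry no timing, so section 3.9 governs them without conflict. Item 5 carries its own timing clause, and that clause disagrees with section 3.9.

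Three things are at stake. Section 2.4 wants between-group effect sizes on every outcome measure to inform a full trial, and evidence that the instruments are sensitive to change; both need a post-ACP form. Agreement is a candidate endpoint for the economic evaluation, so its definition carries over into that work. And with definition, narrative and table pointing to different forms, the choice of form could be made after the data have been seen.

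**Working it through.** No published figure is in dispute and no formula applies. The check is to list each agreement questionnaire in Table 5, class it as before or after ACP using section 3.9, and see which ones the literal definition admits.

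| Group | Questionnaire | Position relative to ACP | Fits the literal definition |
|---|---|---|---|
| Immediate | Baseline | Before | Yes |
| Immediate | 2 weeks, before first review | After | No |
| Immediate | 12 weeks, before second review | After | No |
| Deferred | 12 weeks | Before | Yes |
| Deferred | 24 weeks, before review | After | No |

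**Count.** Immediate 1 + 2 = 3; deferred 1 + 1 = 2; total 5. The literal definition admits 2 of 5, both before ACP, and leaves out 5 − 2 = 3, all after ACP.

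**The contrast under the literal definition.** Immediate group at baseline against deferred group at 12 weeks. Neither side has had ACP, and the two sets of forms are 12 weeks apart.

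**The contrast available in the schedule.** Immediate group at 12 weeks, after ACP, against deferred group at 12 weeks, before ACP. This is a concurrent randomised comparison. With 40 dyads allocated equally there are 40 / 2 = 20 per group, and after the 25% attrition assumed in section 3.4, 20 × 0.75 = 15 per group.

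**Does another section settle which form counts?**
- Section 3.9.a, narrative: it stops at the second assessment, two weeks after ACP. The Time 3 text mentions only the relative/friend's part in the ACP review, so the 12-week questionnaire appears in Table 5 alone.
- Section 4.1.b: agreement is absent from the between-group analysis.
- Section 4.2, benefits: an increase requires at least two readings per dyad, so it contradicts a single pre-ACP reading. It does not say which two.
- Section 2.4: it asks for between-group differences on all outcome measures, but names no form.

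**Can the 12-week comparison be adjusted for baseline?** Table 5 has no relative/friend questionnaire at baseline or 2 weeks in the deferred group, although section 3.9.b says outcomes there are measured at the same times as in the immediate group. As scheduled, a baseline agreement covariate would exist in one group only, so the covariance model used for the other outcomes cannot be fitted. For the same reason the 2-week form has no between-group counterpart.

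**The case against.** The best defence is that the document should be read as a whole. Section 3.8 says what is measured and section 3.9 says when. Section 3.9.a calls the 2-week form a second assessment, so repetition is plainly intended, and item 5 does not restrict itself to a single occasion. The increase in section 4.2 and the between-group effect sizes in section 2.4 point the same way. The timing phrase may be loose wording for an assessment made before the ACP discussion or review, in the manner of the note in Table 5.

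Much of this stands. A reader might infer that the trial cannot show any effect of ACP on agreement, or that the effect is zero by construction. The documents do not support that: the post-ACP forms are scheduled and the 12-week contrast is in Table 5. A reader might also infer that a comparison of pre-ACP forms will be reported as the effect of ACP. No stated analysis does this. Section 4.1.b specifies no between-group test of agreement, and such a comparison would set baseline forms against 12-week forms, contrary to section 3.9.b.

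What the defence does not remove is the contradiction. Table 5 lists the ACP intervention and the ACP review as separate events, and nothing equates the phrase in item 5 with the review. The intent has to be inferred against the stated definition, and even then the endpoint could be the 2-week or the 12-week form.

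**Conclusion.** The stated definition of agreement is wrong for its purpose and conflicts with sections 3.9.a and 4.2 and with Table 5. It selects two pre-ACP questionnaires out of five, and no analysis rule corrects it. The fault lies in the definition; the effect itself can be measured.

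I rate it moderate. This is a feasibility study, agreement is a secondary outcome in Table 3, no progression criterion in section 2.4 depends on its effect, and no data are lost.

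The conclusion rests on these assumptions:
- The Table 5 row with the KDQOL-36 and second review is the 12-week row, as the Time 3 text indicates.
- The 12-week forms in the two groups are concurrent, as section 3.9.b states.
- Table 5, and not the general statement in section 3.9.b, is right that deferred-group relatives/friends complete no baseline form.
- The patient's recorded ACP preferences are the reference for scoring agreement, since Table 5 lists no separate patient form for this.

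Table 3 is the only evidence here of the registered wording; the registry record itself may differ.

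**What to change.** - **Section 3.8 item 5 and Table 3.** Replace the closing timing clause with: *at 12 weeks, from the questionnaire completed before the 12-week ACP review (immediate group) or before any ACP (deferred group)*.
- **Section 4.1.b.** Add agreement as a between-group comparison at 12 weeks with a 95% CI, and state that it is not adjusted for baseline agreement because the deferred group has no baseline relative/friend form.
- **Supportive data.** State that the immediate group's baseline and 2-week forms are supportive, within-group data.
- **Section 3.9.a, Time 3.** Mention the relative/friend questionnaire, so that the text matches Table 5.
- **Section 4.2, benefits.** If agreement is the measure chosen, note that an increase from baseline to 12 weeks can be computed in the immediate group only.
- **Registry.** Align the entry if it carries the same wording as Table 3.

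The cost is an amendment to the wording, plus a registry edit if one is needed. No visit or form is added. The change should be made before agreement data are examined by group.

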3.9. Timeline of Trial Outcome Measures

3.9.a. Immediate Entry Group

Baseline/Time 1: Following enrolment and prior to receiving the intervention, patients randomised to the immediate intervention group will complete the IST 15, CORE 34, and KDQOL-36TM, and SHARED. Their nominated relative/friend will make an independent assessment of the patient's ACP preferences before the patient receives the information booklet. Subsequently, the patient and (if the patient wishes) the relative/friend will participate in the ACP intervention.

Time 2: At two weeks following the intervention, the patient will complete the CORE 34 and SHARED, and review their ACP. The nominated relative/friend will make a second independent assessment of the patient's preferences.

Time 3: At 12 weeks the patient will again complete CORE 34, KDQOL-36™, and SHARED and both patient and relative/friend will review the ACP and make any desired changes.

3.9.b. Deferred Entry Group

Patients (and their nominated relative/friends) randomised to the deferred entry group will have outcomes measured contemporaneously with the immediate entry group but receive the intervention only after they have completed three sets of data i.e. at 12 weeks following entry to the trial. At 24 weeks the deferred entry group patients will again complete CORE 34, KDQOL-36™, and SHARED and both patient and relative/friend will review the ACP and make any desired changes. The deferred entry group may have more than one ACP review with the ACPN, however data will only be collected from this group at the final review.

Table 5: Schedule of Trial Interventions and Assessments

Time points	Immediate entry		Deferred entry	
	Patient *	Relative	Patient*	Relative/friend
t₁ baseline	IST 15 CORE 34 KDQOL-36™ SHARED	ACP agreement questionnaire	IST 15 CORE 34 KDQOL-36™ SHARED	
	ACP intervention	ACP intervention		
2/52	ACP 1 st review CORE 34 SHARED	ACP agreement questionnaire (before review) ACP review**	CORE 34 SHARED	
	CORE 34 KDQOL-36™ SHARED ACP 2 nd review	ACP agreement questionnaire (before review) ACP review**	CORE 34 KDQOL-36™ SHARED	ACP agreement questionnaire
24/52			ACP intervention	ACP intervention
			ACP review**	ACP agreement questionnaire (before

		CORE 34 KDQOL-36™ SHARED	review) ACP review**

Key: IST 15 = Isaacs Set Test CORE 34 = Clinical Outcomes in Routine Evaluation measure KDQOL-36™ = Kidney Disease Quality of Life instrument – Short Form SHARED = Patient Experience of Shared Decision Making instrument
 
* Patients in both groups will also complete a cost diary during intervention period as part of the economic evaluation
 
** Relative/friend may or may not be at the review of the ACP with the patient (this is at the patient and/or relative friend's discretion)
			

4. Methods: Data Analysis and Management

4.2. Economic Evaluation

4.2.a. Outline of the economic analysis

The feasibility of a cost-effectiveness and cost-utility analysis of the ACP intervention compared to usual care, conducted from a societal perspective, will be explored in the pilot study, to inform a full economic evaluation alongside the main trial.

4.2.b. Outcomes for the analysis

The analysis will report the cost per [primary endpoint achieved e.g. relative/friend agreement or SHARED]; and the cost per quality adjusted life year (QALY) gained of the ACP intervention compared to usual care.

4.2.c. Participant utilities

The SF-6D preference based instrument contained within the SF-12 and KDQoL-36 survey will be administered to all patient participants at baseline and 12 weeks. QALY weights (utilities with a value between 0 and 1) from self-reported data will be calculated using UK tariffs (the value set) of the SF-6D. QALYs will be calculated by multiplying the utility with the time spent in that health state using an area under the curve approach. A minimally important difference in utility has been reported at 0.03-0.05. Mean costs (including volume of resource use) and mean health outcomes per allocated group will be reported with 95% confidence intervals. Mean costs will be presented as unadjusted and adjusted for any baseline differences in age, sex, or SES.

4.2.d. Detailed Statistical Analysis of Economic Data

Skewed cost data: Cost data are likely to be right skewed as they are bounded by zero (i.e. can't be negative); have no upper bound, and a small number of patients may incur very high costs, affecting

the mean. The cost distribution will be plotted in a histogram and non-parametric bootstrapping will be used for analysis.

Results: The mean and total volume of major categories of resource use (e.g. hospitalisations; doctor's visits; nurse visits;) will be reported for each group. The difference in the volume of resource use for each group and 95% confidence intervals for the difference will be reported.

Total costs: The total cost will be calculated by multiplying the arithmetic mean cost by the number of participants in each group. Mean costs with standard deviations and total costs for each group will be reported in UK pounds for the most recent reference year. The difference in total costs will be assessed using the student t test and/or analysis of variance (ANOVA). Total costs will also be adjusted for relevant baseline characteristics (e.g. age, sex).

Benefits will include: (i) quality of life, measured at baseline and 12 weeks with the KDQOL-36™ survey; (ii) the proportion of participants with a unit increase in CORE 34; (iii) the proportion of patients with a unit increase in either SHARED or relative/friend Agreement – [whichever will be the primary outcome] (iv) QALY gained at 12 weeks.

Sensitivity analyses: One-way sensitivity analyses will be conducted around key variables including health and social care costs +/- individual patient costs; and health system resource use as measured in patient diaries compared to the base case measurement using hospital administrative records.

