3.3. Eligibility Criteria

Eligible patients will be randomised in equal proportions between the immediate and deferred entry groups.

Patient's eligibility criteria:

- English speaking
- Attending the renal units above
- Aged 65 years or more; with ESKD and receiving RRT

- Capacity to understand, retain, and weigh the necessary information in English and communicate their decisions¹⁰
- Identified by their consultant as having either worsening symptoms, functional decline, or two or more co-morbidities
- Not expected to die in the next three months

Relative/friend eligibility criteria:

- Aged 18 years or older
- Ability to read, write, and speak English
- Identified by the patient as their nominated relative/friend and willing to represent the patient's wishes should they lose decision-making capacity

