3.4. Sample size

Forty patient-relative/friend dyads will be recruited onto the trial. Assuming 25% attrition⁴⁴, this sample size is thought to provide sufficient numbers to allow feasibility to be estimated, and to offset the bias in estimates of effect size produced by very small samples^{45,46}.

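### A cost per QALY will be reported from about 15 patients per arm with no interval or joint cost-QALY uncertainty for the ratio

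*Combined protocol and SAP*

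**What the plan says.** Section 4.2.a presents the economic work as preparatory: "The feasibility of a cost-effectiveness and cost-utility analysis of the ACP intervention compared to usual care" is to be explored in order to inform the main trial. Section 4.2.b goes further and says the analysis will report two ratios. One is a cost per primary endpoint achieved. The other is "the cost per quality adjusted life year (QALY) gained of the ACP intervention compared to usual care".

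Under 4.2.c, SF-6D utilities are collected at baseline and 12 weeks and turned into QALYs by area under the curve. The same section gives the only effect size for utility: "A minimally important difference in utility has been reported at 0.03-0.05". The benefits listed in 4.2.d include "QALY gained at 12 weeks", and section 3.8 limits the costing to a "comparison of mean costs per patient by group allocation for the 12 week period of the trial".

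Uncertainty is covered in four ways:
- 95% CIs for mean costs and mean health outcomes in each group
- CIs for differences in the volume of resource use, and a t test or ANOVA on costs
- non-parametric bootstrapping, placed under the item on skewed cost data
- one-way sensitivity analyses

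Costs are to be adjusted for baseline characteristics such as age, sex or SES. No adjustment of QALYs for baseline utility is stated. The ANCOVA in 4.1.b covers CORE 34, KDQOL-36 and SHARED scores, not QALYs.

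**The concern.** A ratio behaves badly when its denominator is small relative to its standard error. Small changes in the data then produce very large positive or negative values. A negative value is also ambiguous, because it can mean cheaper and better or dearer and worse. Separate intervals for each group's mean cost and mean QALY do not give the uncertainty of the ratio, which also depends on the correlation between cost and QALY within patients.

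The plan states no interval for the ratio, no joint resampling, no cost-effectiveness plane, no net benefit and no rule for a QALY difference near zero or below it. What is at stake is a published cost per QALY that readers cannot interpret and later work might cite as an estimate.

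**Working it through.** **Inputs from the documents**
- Section 3.4: "Forty patient-relative/friend dyads will be recruited onto the trial", and "Assuming 25% attrition".
- Section 3.3: "Eligible patients will be randomised in equal proportions between the immediate and deferred entry groups".
- Horizon: 12/52 = 0.2308 years, with utility at two times only (4.2.c).
- Utility difference d at 12 weeks: 0.03 to 0.05 (4.2.c).

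**Inputs assumed, because the documents give neither**
- Utility SD s: 0.08 to 0.15.
- Baseline to 12-week correlation r: 0.5 to 0.8.

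**Completers.** 40 × 0.75 = 30, or 15 per arm if losses are equal. The plan gives no precision or power figure for QALYs, so there is none to reproduce.

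**Size of the denominator.** With two utility measurements, QALY = (12/52) × (u0 + u12)/2. Starting from equal expected baselines, the expected difference is 0.5 × d × 12/52:
- d = 0.03: 0.5 × 0.03 × 0.2308 = 0.0035 QALY, about 1.3 quality-adjusted days
- d = 0.05: 0.5 × 0.05 × 0.2308 = 0.0058 QALY, about 2.1 quality-adjusted days

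**Precision as the plan is written (no baseline-utility adjustment).** SE = (12/52) × s × √((1 + r)/2) × √(2/15). The half-width is SE × 2.05 (t, 28 df). The probability of the wrong sign is Φ(−difference/SE).

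| s, r | SE | 95% half-width | Wrong sign, d = 0.03 | Wrong sign, d = 0.05 |
|---|---|---|---|---|
| 0.08, 0.5 | 0.0058 | 0.012 | 28% | 16% |
| 0.12, 0.6 | 0.0090 | 0.019 | 35% | 26% |
| 0.15, 0.8 | 0.0120 | 0.025 | 39% | 32% |

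Middle row in full: 0.2308 × 0.12 × √0.8 × √(2/15) = 0.2308 × 0.12 × 0.894 × 0.365 = 0.0090. Then Φ(−0.0035/0.0090) = 35% and Φ(−0.0058/0.0090) = 26%.

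The half-width is about 2 times (0.012/0.0058) to 7 times (0.025/0.0035) the expected difference. If all 40 patients are retained (20 per arm), the wrong-sign probability is still 13% to 37% across both values of d. With no true effect it is 50%.

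**Precision with adjustment for baseline utility.** SE = 0.5 × (12/52) × s × √(1 − r²) × √(2/15). At s = 0.12 and r = 0.6 this is 0.5 × 0.2308 × 0.12 × 0.8 × 0.365 = 0.0040, with half-width 0.0083 (t, 27 df). The wrong-sign probabilities are 20% (d = 0.03) and 8% (d = 0.05). Over the full assumed range they are 4-26% and 0.2-15%. Adjustment therefore helps a good deal. At 15 per arm, however, an interval centred on the full difference excludes zero only if the residual utility SD is below 0.040 (d = 0.03) or 0.067 (d = 0.05).

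**What this does to the ratio.** Take, purely for illustration, a cost difference fixed at 500 pounds with no sampling error, s = 0.10, r = 0.7, d = 0.03 and baseline adjustment. The true ratio is 500/0.00346, about 144,000 pounds per QALY. The central 95% of estimates runs from about −1.3 million to +1.5 million pounds per QALY, and 12% are negative. This is a favourable case, since real costs add their own sampling error and the plan states no baseline-utility adjustment.

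**The case against.** The strongest reply is that this is a feasibility study of 40 dyads, so imprecision is expected and is not in itself an analysis error. Section 2.4 includes testing methods for assessing cost-effectiveness, and computing a ratio is part of rehearsing them. That stands, and it is why an outright ban on a point ratio would go too far. Reasonable analysts differ on whether to show one.

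It can also be said that both components will be visible, because mean costs and mean outcomes are reported per group with CIs. A reader could then see which component had changed sign. That also stands. Nothing in the plan says the ratio will appear alone. But group-mean intervals do not supply an interval for the ratio.

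The bootstrap sentence could be read generously as covering the ratio. It sits under skewed cost data, however, and does not mention QALYs or pairs.

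Two stronger readings are tempting, and the documents do not support them:
- **That the ratio could tip the decision on a full trial.** The only economic progression criterion in section 2.4 is that an economic evaluation be feasible. No cost or cost-per-QALY threshold exists.
- **That the 12-week horizon makes the ratio miss the benefits expected in section 4.5.** That section attributes those benefits to the full study, and section 2.4 already treats the suitability of the twelve-week deferral as a question for this study. The change proposed here would not alter the horizon either.

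**Conclusion.** The point holds as a gap in the analysis and reporting plan for a secondary component. Section 4.2.b promises a cost per QALY whose denominator would be only 0.0035 to 0.0058 QALY even if the full minimally important difference were reached, and nothing in the plan carries joint uncertainty into the ratio. Across the whole assumed range, the QALY analysis as written has a half-width at least twice the expected difference and a wrong-sign probability of at least 16%.

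The size of the problem rests on the assumed SD and correlation, on equal losses between arms and on a normal approximation. The size of the denominator, and the absence of any stated uncertainty for the ratio, do not depend on the assumed SD and correlation. The consequence is an uninterpretable published number. The feasibility conclusions and the progression decision are not threatened.

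**What to change.** Keep the cost-per-endpoint clause in 4.2.b. Replace only the QALY clause with wording such as:

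> Incremental cost and incremental QALYs (adjusted for baseline utility) will be reported separately with bootstrap 95% CIs. Cost and QALY pairs will be bootstrapped jointly by patient and shown on the cost-effectiveness plane. Any cost-per-QALY ratio will be labelled exploratory and not presented without this joint uncertainty.

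Also list, as the main economic outputs, the cost diary return rate, SF-6D completion, the SDs of cost and utility, and the cost-QALY correlation. These answer the progression criterion on economic evaluation directly and are what the design of the full trial needs.

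The cost is a change of SAP wording and a little more analysis. No new data are needed, and bootstrapping is already planned for costs. The downside is that the pilot yields no stand-alone headline ratio.
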